7.7 Laboratory Evaluations

Baseline laboratory results as collected on the Local Laboratory eCRF at Screening and Enrollment will be presented in tables by arm and visit and by site and visit. Summary statistics appropriate for continuous variables will be used to describe each of the following: AST (SGOT), ALT (SGPT), and creatinine values. No formal statistical testing will be performed.

8. PRIMARY ENDPOINT ANALYSES

8.1 Adverse Events

For the analysis of the primary safety endpoint, we will present the number and the proportion of participants experiencing at least one Grade 2 or higher adverse event, overall and by study arm. Each participant will contribute once in each category (i.e., only the highest severity AE of each participant) for the calculation of event risks. Exact binomial confidence intervals, using the Pearson-Clopper method, will be provided and Fisher's Exact test will be used to test for differences in risks between the arms.

Additionally, we will also present the following listings and tables of Adverse Events. No formal statistical testing will be conducted.

- The total number (and percentage) of adverse experiences by severity and relationship to study product, overall and for each study arm and for each site.
- Number and percentages of adverse experiences by body system/MedDRA preferred term and severity, by study arm and by site.
- Number and percentages of adverse experiences by body system/MedDRA preferred term and relationship to study product, by study arm and by site.
- Cumulative listing of Adverse Events, with arm, site and participant ID, MedDRA preferred term and AE verbatim, severity, relationship to study product, date reported to site, onset date, outcome date, duration in days, treatment, and outcome.

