2.3.1 Randomization

Participants were randomized in a 2:1 ratio to the dapivirine and placebo arms, stratified by study site.

Participants were also sequentially assigned in a 1:1 ratio to provide intensive PK samples at either 30-60 or 120 minutes after administration of the gel on Visits 3 and 13. Participants were also sequentially assigned in a 1:1:1 ratio to provide intensive PK samples at either Visits 4 and 14, Visits 5 and 15 or Visits 6 and 16.

The randomization scheme has been generated and maintained by the MTN SDMC.

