2.3.3 Sample Size and Power

The proposed sample size for this study was 27 participants, with 18 in the active arm and 9 in the control arm. The study has power to detect only very large differences in safety event rates between active and control arms. With 5% significance level, the study has 85% power to detect a rate in safety endpoint greater than 67% in the active arm when assuming an 11.2% rate in the control arm. On the other hand, the proposed sample size ensures a reasonable frequency of safety events that are not too rare. For example, if the true event rate of an adverse event is 10%, then the probability of observing at least one adverse event in the study is 85%.

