5. GENERAL ANALYSIS METHODS

Descriptive statistics will be used to summarize continuous (mean and standard deviation, median and interquartile range, quartiles, range, and number of missing data values) and categorical (frequencies, relative frequencies, percentages, and number of missing data values) outcomes. Line, scatter, and box plots will be used, as appropriate, to visualize trends in longitudinally repeated measures.

Confidence intervals will be obtained using the Clopper-Pearson method for binary outcomes, while for continuous outcomes these will be based on the Student's-*t* statistic. Unless otherwise specified, 95% confidence intervals will be provided.

When use of formal testing to assess differences between participants in active and placebo arms are required, the following methods will be used: for binomial response variables, a Fisher's exact test; for continuous variables, t-tests or nonparametric methods. Unless otherwise specified, results from two-sided hypothesis tests will be reported.

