6. TRIAL PARTICIPANT DISPOSITION

6.1 Disposition of Participants

Enrollment of participants took place at three study sites: Birmingham, AL, and Pittsburgh, PA, in the US and Bangkok in Thailand.

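### The primary safety comparison ignores the site strata used at randomisation and plans no between-arm risk difference with an interval

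*SAP*

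**What the plan says.** SAP section 2.3.1: "Participants were randomized in a 2:1 ratio to the dapivirine and placebo arms, stratified by study site". Section 6.1 names the strata: "Enrollment of participants took place at three study sites: Birmingham, AL, and Pittsburgh, PA, in the US and Bangkok in Thailand".

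Section 8.1 defines the primary safety analysis. It gives the count and proportion of participants with at least one Grade 2 or higher event, overall and by arm, with Clopper-Pearson intervals. For the comparison, Fisher's "Exact test will be used to test for differences in risks between the arms". Site enters only through descriptive adverse event tables and a listing, without testing. Neither section 8.1 nor the general methods in section 5 names a risk difference, risk ratio or odds ratio. Section 5 fixes the sidedness: "Unless otherwise specified, results from two-sided hypothesis tests will be reported".

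Section 2.3.3 sets 18 active against 9 control and limits the study's power to very large differences: "With 5% significance level, the study has 85% power to detect a rate in safety endpoint greater than 67% in the active arm". The control rate behind that figure is 11.2%.

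**The concern.** There are two gaps of unequal weight.

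**No between-arm estimate.** The p-value is the only between-arm inference planned, in a study that says it can detect only extreme differences. Failing to reject is a likely outcome even if the gel causes appreciable harm. Two separate one-arm intervals do not show how much excess risk remains possible; an interval for the difference does.

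**The stratification factor is dropped without explanation.** Arms are balanced within site, but the test pools sites. If event rates differ between sites, the pooled test allows for between-site variation that the design has removed, and its true type I error falls further below 5%. In a safety comparison, extra conservatism works towards missing harm.

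**Working it through.** **1. The plan's own power figure.** Inputs from section 2.3.3: 67% vs 11.2%, n = 18 and 9, 5% level; two-sided from section 5.

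- Pooled rate = (18 × 0.67 + 9 × 0.112)/27 = 0.484
- Null SE = √[0.484 × 0.516 × (1/18 + 1/9)] = 0.2040
- Alternative SE = √[0.67 × 0.33/18 + 0.112 × 0.888/9] = 0.1528
- z = (0.558 − 1.96 × 0.2040)/0.1528 = 1.035, so power = 85.0%

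The stated 85% is reproduced. Exact enumeration of the two-sided Fisher test that will actually be used gives 82.5%.

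**2. What the missing interval would show.** The Newcombe score-type interval for d = p1 − p2 uses the Wilson limits (l, u) of each arm:

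- lower = d − √[(p1 − l1)² + (u2 − p2)²]
- upper = d + √[(u1 − p1)² + (p2 − l2)²]

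For 6/18 (Wilson 0.163 to 0.563) and 3/9 (0.121 to 0.646), d = 0:

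- lower = −√(0.1705² + 0.3125²) = −0.356
- upper = √(0.2292² + 0.2127²) = 0.313

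Hypothetical outcomes at the planned arm sizes:

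| Active vs control | Fisher p | Difference (points) | 95% CI (points) |
|---|---|---|---|
| 6/18 vs 3/9 | 1.00 | 0 | -36 to +31 |
| 6/18 vs 1/9 | 0.36 | +22 | -14 to +47 |
| 8/18 vs 1/9 | 0.19 | +33 | -5 to +57 |

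The plan would print the p-value but not the last two columns. This step needs no assumption about sites.

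**3. Fisher against stratified tests, planning odds ratio held constant.** The SAP gives neither site sizes nor site event rates. Assumed: 6:3 at each of three sites and a within-site odds ratio of (0.67/0.33)/(0.112/0.888) = 16.1. All outcomes are enumerated, and the null of the stratified test is the convolution of three hypergeometrics.

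| Site control rates | Fisher power | Exact stratified power |
|---|---|---|
| 11.2% at all sites | 82.5% | 80.5% |
| 8/10/16% | 80.7% | 79.1% |
| 5/11/20% | 76.4% | 76.1% |
| 5/10/50% | 62.7% | 67.5% |
| 2/5/27% | 48.9% | 56.4% |
| 2/10/60% | 39.4% | 51.5% |

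With equal sites, the stratified mid-p exact test has 83.3% and the asymptotic Cochran-Mantel-Haenszel (CMH) test 83.9%. At 2/10/60% they have 60.7% and 65.3%.

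**4. The same comparison with overall rates held at 67% and 11.2%.** Site effects of −s, 0, +s on the logit scale:

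| s | Fisher | Exact stratified | CMH |
|---|---|---|---|
| 0 | 82.5% | 80.5% | 83.9% |
| 0.5 | 82.8% | 81.5% | 85.0% |
| 1.0 | 83.5% | 83.9% | 88.1% |
| 1.5 | 84.5% | 86.9% | 91.8% |
| 2.0 | 85.6% | 90.0% | 94.8% |

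Site totals of 12/9/6 and 15/9/3 give the same pattern. The largest loss for the exact stratified test was 2.6 points (79.9% vs 82.5%), at 15/9/3 with equal rates.

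**5. Type I error.** With true site rates of 10/30/60% in both arms, actual size is 1.6% for Fisher, 2.4% for the exact stratified test and 5.05% for CMH. At 2/10/60%, Fisher's is 0.4% and the exact stratified test's 1.9%.

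**The case against.** The case against has real force on the testing side.

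- **Fisher's test is valid here.** Ignoring site does not inflate type I error, and an unstratified exact test is a defensible choice with about nine participants per site. This stands.
- **The exact stratified test is not reliably better.** It is behind Fisher when sites are alike or moderately different. This stands, and it is why Fisher need not be displaced as the primary test.
- **The low Fisher powers in step 3 are mostly not a cost of pooling.** A reader might set 39.4% beside 82.5% and infer that ignoring site halves the power. It does not. With identical sites and the same overall rates, Fisher has 42.8%, 62.1% and 49.4% for the 2/10/60, 5/10/50 and 2/5/27 scenarios, against 39.4%, 62.7% and 48.9%. Nearly all of the fall comes from the changed overall rates. In step 4, with overall rates fixed, Fisher's power does not fall at all.
- **Anyone can compute the difference from the reported counts.** True, but a post hoc interval chosen by a reader does not replace a prespecified one for the primary safety question.

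A reader might also infer that a null result would be uninterpretable. The SAP does not support that. Exact intervals for each arm are planned, the low power is stated openly, and section 8.1 adds tables by severity, relationship, arm and site. The result would be harder to read, not unreadable.

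**Conclusion.** The point holds in two parts.

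The firmer part is the absent between-arm estimate. It rests only on the planned arm sizes: a p-value of 1.00 can accompany an interval of about -36 to +31 points, and a p-value of 0.19 one of about -5 to +57. The plan as written would not display either interval.

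The second part is conditional. The analysis omits the randomisation stratum without giving a reason, which makes a valid test more conservative if sites differ. Against the plain exact stratified test, the effect on power runs from a gain of about 2 points for Fisher (similar sites) to a loss of 4 to 12 points (strong differences). The mid-p and CMH versions matched or exceeded Fisher in the scenarios examined at 6:3 per site, with type I error no higher than about 5%. Site sizes and site rates are assumptions throughout, and the SAP gives no reason to expect strong differences between sites.

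This is a worthwhile, inexpensive improvement to a phase 1 safety analysis, not an error that invalidates it.

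**What to change.** Amend section 8.1 before unblinding:

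1. Report the between-arm risk difference in Grade 2 or higher adverse events, with a 95% score-type or exact interval (name the method), as the main between-arm summary. Keep the Fisher p-value and the per-arm Clopper-Pearson intervals beside it.
2. Add a prespecified site-stratified analysis, either the mid-p exact conditional test or CMH, beside Fisher's test.
3. State how a disagreement between interval and test will be read. It can occur: 9/18 vs 1/9 gives Fisher p = 0.09, while the Newcombe interval is about +0.3 to +62 points and excludes zero.

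The cost is a few lines of SAP text and standard procedure calls, with no new data. The mid-p and asymptotic tests do not strictly guarantee the 5% level (CMH reached 5.05% in step 5), which is a reason to keep Fisher's test alongside them.

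### The descriptive adverse event tables in SAP Section 8.1 count events, state no denominator for their percentages, and so do not show the proportion of participants affected in each arm

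*SAP*

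**What the plan says.** The primary safety analysis in SAP Section 8.1 is per participant. It reports "the number and the proportion of participants experiencing at least one Grade 2 or higher adverse event, overall and by study arm". The same paragraph adds a counting rule for that analysis: "Each participant will contribute once in each category (i.e., only the highest severity AE of each participant) for the calculation of event risks".

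A separate paragraph then opens with "Additionally, we will also present the following listings and tables of Adverse Events. No formal statistical testing will be conducted". Three tables and a cumulative listing follow. The first table cross-classifies adverse experiences, as counts and percentages, on severity and on relationship to product, for the whole study and split by arm and site. The second is set out as "Number and percentages of adverse experiences by body system/MedDRA preferred term and severity, by study arm and by site". The third keeps the layout of the second but puts relationship to product in place of severity.

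None of the three mentions participants, a count-once rule or a denominator. Section 10.1 only refers back to Section 8, so the SAP specifies no other table by term, severity or relationship.

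**The concern.** The unit in these tables appears to be the event. Elsewhere the SAP names the unit of its percentages: participant-visits in Section 6.1.5, samples in Section 8.2.1, and participants in Sections 7.5 and 10.3.1. Where it writes adverse experiences in three consecutive bullets, events are the natural reading.

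A percentage of events answers a different question from the one a safety reader asks, which is what share of the people dosed in each arm had this event, or had one judged related to product. Participants receive eight doses (one single dose, then seven daily doses), so one person can report the same term several times. With planned arms of 18 and 9, one such person can dominate a row. Section 2.3.3 also concedes power for only very large differences, so these descriptive tables will carry much of the reading of which events occurred and in which arm. As specified, none of them gives participant proportions by term or by relationship.

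**Working it through.** The plan gives no figure of its own on this point to reproduce. The inputs from the SAP are the arm sizes, 18 dapivirine and 9 placebo (Section 2.3.3), and the 2:1 ratio (Section 2.3.1). **All event counts below are assumed**, because the SAP gives none. They show what each possible denominator can do and do not predict the trial's results.

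The target quantity is participants with at least one event of the term, divided by participants dosed in the arm.

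**1. Denominator = all events in the same arm, with repeats.** Dapivirine: 6 participants with one event each, 30 events of any kind in the arm. Placebo: 1 participant with 4 repeats, 10 events of any kind.
- Participants: 6/18 = 33.3% versus 1/9 = 11.1%.
- Events: 6/30 = 20.0% versus 4/10 = 40.0%. The ordering reverses.

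**2. Same denominator, no repeats.** Dapivirine: 6 participants, 30 events in the arm. Placebo: 2 participants, 6 events in the arm.
- Participants: 6/18 = 33.3% versus 2/9 = 22.2%.
- Events: 6/30 = 20.0% versus 2/6 = 33.3%. The ordering reverses again, this time only because total event burden differs (30/18 = 1.67 versus 6/9 = 0.67 events per participant).

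**3. What drives cases 1 and 2.** For an arm of size n, let m be the mean number of events of the term per participant and r the mean number of events of any kind per participant. The within-arm percentage is (m × n)/(r × n) = m/r. Arm size cancels, so the allocation ratio plays no part. The ratio of the two arms' percentages is (m_active/m_placebo) × (r_placebo/r_active).
- Case 1: (0.333/0.444) × (1.11/1.67) = 0.75 × 0.667 = 0.50, which matches 20%/40%.
- Case 2: (0.333/0.222) × (0.67/1.67) = 1.5 × 0.4 = 0.60, which matches 20%/33.3%.

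**4. Denominator = all events of the term, both arms pooled, no repeats.** Here allocation does matter.
- Equal risks, 6/18 = 33.3% and 3/9 = 33.3%, show as 6/9 = 66.7% versus 3/9 = 33.3%.
- Higher placebo risk, 6/18 = 33.3% versus 4/9 = 44.4%, shows as 6/10 = 60% versus 4/10 = 40%, which is reversed.

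**5. Denominator = participants, but numerator = events.** In case 1 this gives 6/18 = 33.3% versus 4/9 = 44.4%, although only 1/9 = 11.1% of placebo participants were affected. The numerator therefore has to be fixed as well as the denominator.

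**6. Not every choice reverses the order.** In case 1, percentages over all 40 events of both arms are 6/40 = 15% versus 4/40 = 10%. The order is kept, but a threefold ratio of risks (33.3%/11.1%) shrinks to 1.5.

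**The case against.** **The denominator is unstated, not wrong.** A reader might infer that the SAP fixes the arm's own event total as the denominator. It does not say so, and several bases are possible. This stands. The point is an event-level count with an unspecified denominator, and the examples cover the candidates.

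**The count-once rule may extend to the tables.** A yes/no endpoint needs no reference to each category or to highest severity, so that wording would suit tables by severity. The ambiguity is real. But the sentence sits in the primary endpoint paragraph and is tied to event risks, and the tables are introduced afterwards as additional. Its parenthesis keeps one event per person, so applied literally to a table by term it would drop all of that person's other events. If participant counting was intended, the bullets need the same edit.

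**Allocation is not the general cause.** A reader might infer that the 2:1 ratio makes the arm percentages point the wrong way. Step 3 shows that it cancels with within-arm denominators; it distorts only percentages pooled across arms.

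**The arms can still be compared.** A reader might infer that a comparison by term is impossible. The planned cumulative listing carries arm, participant ID, preferred term, severity and relationship, so with about 27 participants the counts can be rebuilt by hand. The tables also show event numbers beside the percentages, and Section 10.3.1 gives participant-level anorectal examination findings. All of this stands and limits the consequence. It does not close the gap, since a listing is not a summary and examination findings are not adverse events classified by relationship.

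**The tables are descriptive and untested.** This stands too.

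**Conclusion.** The point holds as one of presentation. Followed as written, the three tables give event-level percentages over an unstated base. Under plausible bases these can reverse the arm ordering (33.3% versus 11.1% of participants shown as 20% versus 40% of events) or create a difference where there is none (equal risks shown as 66.7% versus 33.3%). The sizes rest on assumed counts and on the planned arms of 18 and 9. The conclusion that such percentages do not estimate the proportion of participants affected does not depend on those counts.

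The consequence is confined to descriptive safety summaries. The primary endpoint is already per participant, with exact intervals and Fisher's exact test, and no endpoint, test or power figure changes. The absence of a separate row for product-related Grade 2 or higher events is not an error, because the endpoint in Section 2.2 is defined without relationship to product.

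**What to change.** In the three table bullets of Section 8.1:

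- Report the number and percentage of participants with at least one event.
- Count each participant once per term, at highest severity in the severity tables and at strongest relationship in the relationship tables.
- Use as denominator the participants in that arm or site who received at least one dose, which is the safety analysis set of Section 3.1.
- Show the number of events in an adjacent column, without a percentage.

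A row for participants with a product-related Grade 2 or higher event, by arm, is optional and is not needed to correct the tables.

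The cost is a few lines of SAP wording and a change of numerator and denominator in the table programs. The listing already requires all the data items used, so nothing new is collected. This is a free improvement.

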8.2 Pharmacokinetics Evaluations

8.2.1 Dapivirine concentrations in blood, rectal fluid and rectal tissue

For participants in the active arm only, we will report the dapivirine concentration in blood at all time points where a sample was obtained. At each sampling time point, the concentration of dapivirine will be summarized using descriptive statistics (mean, standard deviation, median, interquartile range and range, along with number of participants). Also, 95% confidence intervals for the mean concentration will be obtained, using a Student's-t distribution approximation. Given the small number of samples that are expected for some sampling points, a log transformation of the concentrations will be considered if the data suggest strong skewness. No formal statistical testing will be performed.

For concentrations of dapivirine that fall below the corresponding assay's lower limit of quantification (LLOQ), we will use a value equivalent to half the LLOQ of the assay. The number and percentage of samples that fall below the LLOQ for any given sampling time point will be reported.

The time-points in the proposed sampling schedule were selected to roughly provide a description of some important PK characteristics. The sample taken 30-60 min after dosing time will be used to describe the concentrations soon after a gel dose. The sample taken 2 h after dosing will be used to roughly approximate peak concentrations. Concentrations from 2 h, 24h, 48 h and 72 h after dosing will be used to estimate terminal elimination half-life. The sample taken at dosing time after multiple doses will be used to estimate the concentration accumulation with multiple dosing (approach to steady state).

The following figures and tables are planned to describe the concentration of dapivirine in blood, rectal fluid and rectal tissue:

Dapivirine concentrations in blood

- Table summarizing the concentration of dapivirine after single dose: at time of dosing (visit 3), 30-60 min (visit 3), 120 min (visit 3), 24 h (visit 4), 48 h (visit 5) and 72 h (visit 6) after the time of dosing.
- Table summarizing the concentration of dapivirine after the first of multiple doses: at time of dosing (visit 7) and 24 h after time of dosing (visit 8).
- Table summarizing the concentration of dapivirine after multiple doses: at time of dosing (visit 13), 30 – 60 min (visit 13), 120 min (visit 13), 24 h (visit 14), 48 h (visit 15) and 72 h (visit 16) after time of dosing.

- Individual concentration profiles for each participant (dapivirine concentration in blood over time), after single dosing (Visits 3 to 6) and multiple dosing (Visits 13 to 16) overlaid in one plot per participant.
- Individual concentration profiles after single dosing (Visits 3 to 6) for all participants, overlaid on a single plot.
- Individual concentration profiles after multiple dosing (Visits 13 to 16) for all participants, overlaid on a single plot.
- Plot of the median of dapivirine concentration in blood over time, with vertical bars indicating 95% confidence interval. Separate plots for concentrations after single and after multiple dosing, as well as overlaid on a single plot.

Dapivirine concentrations in rectal fluid and rectal tissue

- Table summarizing the concentration of dapivirine after single dose: at 30-60 min (visit 3), 120 min (visit 3), 24 h (visit 4), 48 h (visit 5) and 72 h (visit 6) after the time of dosing.
- Table summarizing the concentration of dapivirine (in rectal fluid only) after the first of multiple doses: at time of dosing (visit 7) and 24 h after time of dosing (visit 8).
- Table summarizing the concentration of dapivirine after multiple doses: at 30-60 min (visit 13), 120 min (visit 13), 24 h (visit 14), 48 h (visit 15) and 72 h (visit 16) after time of dosing.
- Individual concentration profiles, before and after dosing, overlaid on a single plot for each different sampling schedule.
- Plot of the median of dapivirine concentration in rectal fluid and rectal tissue over time, with vertical bars indicating 95% confidence interval. Separate plots for concentrations after single and after multiple dosing as well as overlaid on a single plot.

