8.2.2 Elimination constant rate and terminal elimination half-life

To determine the terminal elimination half-life of dapivirine from blood, we will use the dapivirine concentrations from samples at 24 h, 48 h and 72 h after the time of dosing. To determine the terminal elimination half-life of dapivirine from rectal fluid and rectal tissue, for each participant we will use their concentration at 120 min after dosing and their concentration at either 24 h, 48 h or 72 h after dosing. Given the sampling schedule, only about half of the participants will have concentrations of rectal fluid and rectal tissue at two of these sampling time points available.

For the calculation of the terminal elimination half-life, for each participant, we will assume a mono-compartmental model, with the concentration at time t given by:

$$C(t) = a e^{-\beta t}$$

To estimate each participant's elimination rate constant (β), we will use linear regression on the log-transformed concentrations of dapivirine, with time (of sampling) as predictor, along with an indicator for samples obtained after multiple dosing. The resulting absolute value of the slope will correspond to the elimination rate constant β . The terminal elimination half-life for each participant will be calculated from the elimination rate constant as

$$t_{1/2} = \frac{\log(2)}{\beta}$$

We will summarize terminal elimination half-life ($t_{1/2}$) for blood, rectal fluid and rectal tissue, using descriptive statistics and will provide a 95% confidence interval, using a Student's-t distribution approximation.

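### Half-LLOQ substitution carries into the half-life regression, so a late sample below the LLOQ can partly or wholly fix a participant's slope, with bias in either direction

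*SAP*

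**What the plan says.** SAP section 8.2.1 covers dapivirine in blood, rectal fluid and rectal tissue. For any concentration below the assay's limit, "we will use a value equivalent to half the LLOQ of the assay". The rule is not restricted by time point, number of samples or analysis. The same section adds that "The number and percentage of samples that fall below the LLOQ for any given sampling time point will be reported".

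Section 8.2.2 derives each participant's elimination rate: "we will use linear regression on the log-transformed concentrations of dapivirine, with time (of sampling) as predictor", together with an indicator for samples taken after multiple dosing. Each participant therefore has one slope common to both dosing periods. The absolute slope is taken as the elimination rate constant, and half-life is log(2) divided by it. The half-lives are summarised descriptively with a Student's-t 95% interval.

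For blood, section 8.2.2 states "we will use the dapivirine concentrations from samples at 24 h, 48 h and 72 h after the time of dosing". For rectal fluid and tissue each participant contributes "their concentration at 120 min after dosing and their concentration at either 24 h, 48 h or 72 h after dosing", and the SAP expects that "only about half of the participants will have concentrations of rectal fluid and rectal tissue at two of these sampling time points available". Section 2.3.1 assigns the later visit 1:1:1.

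Section 8.2.2 does not repeat the half-LLOQ rule, but nothing there suspends it. It also sets no minimum number of quantifiable samples and no sensitivity analysis for unquantifiable ones.

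**The concern.** On a declining curve the latest samples are the most likely to fall below the LLOQ, and they carry most of the information on the terminal slope. Half the LLOQ is a tolerable placeholder in a table of concentrations. In a log-linear regression it acts as a measured value, at a time when all that is known is that the concentration was below the limit.

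The rectal case is the most exposed. A dosing period supplies only two points, and if the later one is a constant, nothing measured at that visit enters the slope. About half of the 18 active participants (section 2.3.3), so about 9, are expected to have a usable rectal pair. A few such values can move the mean half-life and its interval, and the shift depends on which late visit each participant was assigned.

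**Working it through.** The SAP states no half-life, LLOQ, expected concentration or rate of unquantifiable samples, so there is no figure of its own to reproduce. The check applies the section 8.2.2 estimator to noise-free mono-exponential profiles, with concentrations in units of the LLOQ and every value below 1 replaced by 0.5. The concentrations, true half-lives and accumulation factors are assumptions.

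**Rectal fluid or tissue, samples at 2 h and T.** When the later sample is below the LLOQ in both dosing periods and there is no accumulation:

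t½ = ln2 × (T − 2) / ln(2 × C2h/LLOQ)

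The true elimination rate does not appear. With C2h = 100 x LLOQ and a true half-life of 3 h, the later samples are all below the LLOQ (the 24 h value is 0.62 x LLOQ). With ln 200 = 5.298:

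- T = 24 h: 0.693 × 22 / 5.298 = 2.9 h
- T = 48 h: 0.693 × 46 / 5.298 = 6.0 h
- T = 72 h: 0.693 × 70 / 5.298 = 9.2 h

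With threefold accumulation, C2h after multiple dosing is 300 x LLOQ. The sampling times are the same in both periods, so the common slope is the average of the two period slopes. The results are 2.9, 5.5 and 8.3 h. At the 24 h visit the multiple-dose sample is then quantifiable (1.86 x LLOQ), which pulls that result toward the truth. At 48 and 72 h both samples remain below the limit.

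**Effect on the reported summary.** Assume 9 active participants with pairs, three per late visit:

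- No accumulation: mean 6.0 h, SD 2.72, SE 2.72/√9 = 0.91, t(8) = 2.306, 95% CI 3.9 to 8.1 h.
- Threefold accumulation: mean 5.6 h, 95% CI 3.8 to 7.3 h.

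Both intervals exclude the true 3 h.

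**Blood, samples at 24, 48 and 72 h.** On equally spaced times the regression weights are proportional to −1, 0 and +1. The 48 h value has no influence on the slope; the 24 h and 72 h values determine it. Without accumulation, a 72 h sample below the LLOQ gives t½ = 48 × ln2 / ln(2 × C24/LLOQ).

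- C24 = 2 x LLOQ: 48 × 0.693 / ln 4 = 24.0 h, whether the true value is 12 or 16 h.
- C24 = 1.5 x LLOQ: 48 × 0.693 / ln 3 = 30.3 h, for true values of 8, 12, 24, 36, 60 and 80 h alike. The bias is upward for the shorter half-lives and downward for the longer ones.

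With mono-exponential accumulation over 7 daily doses, the factor is the sum of 2^(−24k/t½) for k = 0 to 6: 1.33 for 12 h and 1.55 for 16 h. At C24 = 2 x LLOQ the common-slope regression then gives:

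- True 12 h: period slopes ln(4)/48 = 0.0289 and ln(5.33)/48 = 0.0349, average 0.0319, t½ = 21.7 h.
- True 16 h: period slopes 0.0289 and ln(6.18)/48 = 0.0380, average 0.0334, t½ = 20.7 h.

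**All samples below the LLOQ.** Every value used is 0.5, the slope is zero and log(2)/0 is undefined. The SAP does not say how such a participant enters the mean and the t interval.

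**The case against.** The strongest reply is that the extent is unknown and may be small. If the influential samples are quantifiable, the substitution changes nothing. At C2h = 100 x LLOQ a 24 h rectal sample falls below the limit only if the half-life is under 22 × ln2/ln(100) = 3.3 h. With a true half-life of 6 h and no accumulation, the method returns 6.0, 6.0 and 9.2 h at the three visits; with 10 h it returns 10.0, 10.0 and 9.2 h. The threefold spread above is therefore close to a worst case. A quantifiable second dosing period also dilutes the effect through the common slope. All of this stands, and it limits the size of the point without removing it.

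A reader might infer that the half-life is set by the assay limit and the visit schedule instead of by the drug, or that the reported half-life and its interval will be wrong. The SAP does not support either. The measured 2 h or 24 h concentration still enters, and the error arises only when influential samples are unquantifiable. A reader might also suppose that equal substituted values at 48 and 72 h flatten the blood slope. They do not, because the 48 h value has no weight on these times. Nor is every substitution harmful: with C24 = 2 x LLOQ, a true half-life of 24 h and no accumulation, the 72 h concentration really is half the LLOQ and the method returns 24.0 h.

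It is also fair that half-life is a descriptive quantity derived from the primary PK endpoint, which is the concentrations themselves (section 2.2), and that no formal testing of the concentrations is planned. Reporting the percentage below the LLOQ will show where substitution occurred, but it does not correct the half-lives.

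**Conclusion.** The point holds in conditional form. As written, the half-LLOQ rule reaches the half-life regression. The substituted constant then partly or wholly determines the slope when the 72 h (or 24 h) blood sample or the single later rectal sample is below the LLOQ. The bias can go either way.

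In the rectal scenario a true half-life of 3 h is summarised as about 6 h, with an interval that excludes 3 h. In blood, true values of 12 and 16 h come out at roughly 21 to 24 h. These sizes rest on noise-free mono-exponential profiles, the stated multiples of the LLOQ, the stated accumulation and, for the rectal mean, three participants per late visit. The number of participants affected cannot be judged from the SAP.

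This should be fixed before the half-lives are computed. It does not threaten the primary concentration summaries or the safety analysis.

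**What to change.** Limit the half-LLOQ rule in section 8.2.1 to the descriptive concentration tables, and add to section 8.2.2:

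- Substituted values do not enter the half-life regression. Values below the LLOQ are treated as left-censored at the LLOQ in the log-linear regression.
- A rectal pair whose late sample is below the LLOQ is reported as an upper bound, t½ < ln2 × (T − 2)/ln(C2h/LLOQ). At C2h = 100 x LLOQ this is below 3.3, 6.9 or 10.5 h for T = 24, 48 or 72 h. Each bound contains the 3 h used above.
- An individual point estimate is given only with at least two quantifiable times after a dose. The numbers bounded only and not estimable are reported.
- Half-life is summarised by a method that keeps the bounded participants, for example a median allowing for censoring, or a pooled censored model if it converges. Simply dropping them would remove the fast eliminators and bias the mean upward.

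At the same time, reconcile the blood sampling times: section 8.2.1 says "Concentrations from 2 h, 24h, 48 h and 72 h after dosing will be used to estimate terminal elimination half-life", while section 8.2.2 leaves out 2 h for blood. Adding that point would change which samples carry weight.

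The cost is a short wording change and a censored fit. Fewer participants will have an individual point estimate, the summary will be less precise, and with about 9 rectal pairs a pooled model may not be stable, so the censored median should be named as the fallback.
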